5.5.2 Prohibited Concomitant Medications

Participants are prohibited from receiving the following therapies during the Screening and Treatment Phase (including retreatment for post-complete response relapse) of this trial:

- Antineoplastic systemic chemotherapy or biological therapy

Confidential

Page 30 of 87

- Immunotherapy not specified in this protocol
- Chemotherapy not specified in this protocol
- Investigational agents other than pembrolizumab and olaparib
- Radiation therapy

Note: Radiation therapy to a symptomatic solitary lesion or to the brain may be allowed at the investigator's discretion.

- Live vaccines within 30 days prior to the first dose of study treatment and while participating in the study. Examples of live vaccines include, but are not limited to, the following: measles, mumps, rubella, varicella/zoster, yellow fever, rabies, BCG, and typhoid vaccine. Seasonal influenza vaccines for injection are generally killed virus vaccines and are allowed; however, intranasal influenza vaccines (eg, FluMist®) are live attenuated vaccines and are not allowed.
- Systemic glucocorticoids for any purpose other than to modulate symptoms from an event of clinical interest of suspected immunologic etiology. The use of physiologic doses of corticosteroids may be approved after consultation with the Sponsor.

Participants who, in the assessment by the investigator, require the use of any of the aforementioned treatments for clinical management should be removed from the study. All treatments that the Investigator considers necessary for a participant's welfare may be administered at the discretion of the Investigator in keeping with the community standards of medical care.

Medications or vaccinations specifically prohibited in the exclusion criteria are not allowed during the ongoing study. If there is a clinical indication for any medication or vaccination specifically prohibited during the study, discontinuation from study therapy or vaccination may be required. The final decision on any supportive therapy or vaccination rests with the investigator and/or the participant's primary physician. However, the decision to continue the participant on study treatment requires the mutual agreement of the investigator, the Sponsor and the participant. However, the decision to continue the participant on study intervention requires the mutual agreement of the investigator, the Sponsor, and the participant.

Medications that may NOT be administered

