5.6 Participant Discontinuation Criteria

Discontinuation of study intervention does not represent withdrawal from the study.

Participants may discontinue study treatment at any time for any reason or be dropped from the study treatment at the discretion of the investigator should any untoward effect occur. In addition, a participant may be discontinued from study treatment by the investigator or the Sponsor if study treatment is inappropriate, the trial plan is violated, or for administrative and/or other safety reasons. Specific details regarding procedures to be performed at study treatment discontinuation are provided in Section 7.1.4 – Other Procedures.

A participant must be discontinued from study treatment but continue to be monitored in the study for any of the following reasons:

- The participant or participant's legally acceptable representative requests to discontinue study treatment
- Confirmed radiographic disease progression outlined in Section 7.1.2.6
- Any progression or recurrence of any malignancy, or any occurrence of another malignancy that requires active treatment
- Unacceptable adverse experiences as described in Section 5.2.2.
- The participant has a medical condition or personal circumstance which, in the opinion of the investigator and/or sponsor, placed the participant at unnecessary risk from continued administration of study treatment.
- The participant has a confirmed positive serum pregnancy test
- Noncompliance with study treatment or procedure requirements
- Recurrent Grade 2 pneumonitis
- Discontinuation of treatment may be considered for participants who have attained a confirmed complete response (CR) and have been treated for at least 8 cycles (at least 24 weeks), receiving 2 cycles of the combination including 2 doses of pembrolizumab and at least 80% of the planned doses of olaparib beyond the date when the initial CR was declared. These participants may be eligible for second course treatment described in Section 5.2.3.
- The participant is lost to follow-up
- Completion of 35 treatments (approximately 2 years) with pembrolizumab

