5.7 Participant withdrawal From Study

A participant must be withdrawn from the study if the participant or the participant's legally acceptable representative withdraws consent from the study.

If a participant withdraws from the study, they will no longer receive study intervention or be followed at scheduled protocol visits.

Specified details regarding procedures to be performed at the time of withdrawal from the study as well as specific details regarding withdrawal from future biomedical research are outlined in Sections 7.1.4.1 and 7.1.4.2.

Discontinuation of Study Therapy after CR

Discontinuation of treatment may be considered for subjects who have attained a confirmed CR that have been treated for at least 24 weeks with pembrolizumab or the combination and had at least two treatments with pembrolizumab beyond the date when the initial CR was declared.

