6.1.5.3.3 Survival Follow-up

Participants who experience confirmed disease progression or start a new anticancer therapy, will move into the Survival Follow-Up Phase and should be contacted by telephone every 12 weeks to assess for survival status until death, withdrawal of consent, or the end of the trial, whichever occurs first.

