As per international guidance on anti-emetic use in cancer patients (ESMO, NCCN), generally a single agent antiemetic should be considered e.g., dopamine receptor antagonist, antihistamines or dexamethasone.

Interruptions for intercurrent non-toxicity related events

Study treatment dose interruption for conditions other than toxicity resolution should be kept as short as possible. If a patient cannot restart study treatment within 4 weeks for resolution of intercurrent conditions not related to disease progression or toxicity, the case should be discussed with AZ study physician.

All dose reductions and interruptions (including any missed doses), and the reasons for the reductions/interruptions are to be recorded in the eCRF.

Study treatment should be stopped at least 3 days prior to planned surgery. After surgery study treatment can be restarted when the wound has healed. No stoppage of study treatment is required for any needle biopsy procedure.

Study treatment should be discontinued for a minimum of 3 days before a patient undergoes radiation treatment. Study treatment should be restarted within 4 weeks as long as any bone marrow toxicity has recovered.

Because the AEs related to olaparib may include asthenia, fatigue and dizziness, patients should be advised to use caution while driving or using machinery if these symptoms occur.

Table 14 Dose reductions for study treatment

Initial Dose	Following re-challenge post interruption: Dose reduction 1	Dose reduction 2
300 mg twice daily	250 mg twice daily	200 mg twice daily

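### The removal clause in section 5.5.2 contradicts the plan's own follow-up rules and, read literally, could cut short survival and disease follow-up for patients who need a prohibited treatment

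*Combined protocol and SAP*

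**What the plan says.** Section 5.5.2 opens by limiting its scope: "Participants are prohibited from receiving the following therapies during the Screening and Treatment Phase". The list covers systemic antineoplastic, immune and investigational therapy, radiation, live vaccines and systemic glucocorticoids, some with exceptions. It then states that participants who, in the investigator's assessment, "require the use of any of the aforementioned treatments for clinical management should be removed from the study".

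Other text deals with the same or overlapping patients:

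- The next paragraph of 5.5.2 (and 5.5 in near-identical terms) says of prohibited medication that "discontinuation from study therapy or vaccination may be required", and adds that "the decision to continue the participant on study treatment requires the mutual agreement of the investigator, the Sponsor and the participant".
- Section 5.6: "Discontinuation of study intervention does not represent withdrawal from the study". Patients taken off treatment for the reasons it lists continue to be monitored.
- Section 5.7 makes withdrawal of consent the only ground for mandatory withdrawal. Of those who withdraw it says "they will no longer receive study intervention or be followed at scheduled protocol visits".
- Section 6.1.5.3.3: "Participants who experience confirmed disease progression or start a new anticancer therapy, will move into the Survival Follow-Up Phase", with telephone contact every 12 weeks. Section 6.1.1.6.3 says the same of new anticancer therapy.
- Section 2.0 plans follow-up for three years or until death.

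In section 7.2, OS is censored at the date last known alive and PFS at the last valid disease assessment. A missing response counts as a failure for iORR.

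**The concern.** The protocol separates leaving treatment from leaving the study. The 5.5.2 clause uses the second idea where the surrounding sections use the first. Two sites could therefore handle the same patient differently: one keeps telephoning every 12 weeks, the other closes the record.

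Where the record is closed, deaths and progressions after that date are not captured, and the Kaplan-Meier estimates treat the patient as if she had the same outlook as those still followed. Several triggers (chemotherapy, radiation, steroids) plausibly go with a worse outlook. If so, the censoring is informative and the estimates are too favourable. Uncollected deaths may not be recoverable at analysis.

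The clause also catches care that the protocol describes elsewhere, so the trigger is itself unclear.

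**Working it through.** **1. The primary design reproduces and is not at issue.** Inputs from 7.2: n = 48, success at 10 or more responses, p0 = 0.130, p1 = 0.280.

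- P(X ≥ 10 | 48, 0.13) = 0.0865 (stated 0.087).
- P(X ≤ 9 | 48, 0.28) = 0.09946 (stated 0.099).

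A removed patient with no response recorded stays in the denominator as a failure. This can only lower the response count, so it cannot raise the type I error. Section 6.1.2.6.3 also asks for imaging at treatment discontinuation, and 5.8 for an attempt to assess response in all enrolled patients.

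**2. The rules side by side.**

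| Place | Study treatment | Study participation |
|---|---|---|
| 5.5.2, removal clause | ends by implication | ends |
| 5.5.2 next paragraph; 5.5 | may stop, or continue by agreement | not ended |
| 5.6 | stops for listed reasons | continues |
| 5.7 | ends | ends, on withdrawal of consent |
| 6.1.1.6.3; 6.1.5.3.3 | new anticancer therapy started | continues as survival follow-up |

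The first row cannot be squared with the second, third and fifth.

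**3. Which endpoints are exposed.** If the trigger is a new anticancer drug, disease assessment already ends there under 5.6, 6.1.2.6.3 and 6.1.5.3.2. The clause then adds a loss for OS but little for PFS. If the trigger is a steroid, a live vaccine or some radiation, the other sections would keep imaging going, so PFS is exposed as well as OS. DoR is exposed in the same way if it is censored like PFS; 7.2 gives no separate rule for it.

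**4. Illustration for 12-month OS.** All inputs are assumptions, none from the documents. Of 48 patients, 48 − k have exponential survival with median 12 months. The other k are alive when removed, uniformly between months 1 and 6, and then have residual median m months.

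If everyone is followed, 12-month survival in the k patients is

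c = (1/5) × (m / ln 2) × (2^(−6/m) − 2^(−11/m)).

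For m = 3, c = 0.2 × 4.328 × (0.2500 − 0.0787) = 0.148. Overall survival is [(48 − k) × 0.5 + k × c] / 48:

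- k = 5: (21.5 + 0.74)/48 = 0.463
- k = 10: (19 + 1.48)/48 = 0.427
- k = 14: (17 + 2.07)/48 = 0.397

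If the k patients are censored at removal, the Kaplan-Meier product ∏(1 − d/n) loses their deaths. Simulated with m = 3 (3,000 replicates):

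| k | Followed | Censored | Overstatement |
|---|---|---|---|
| 5 | 0.462 | 0.511 | 4.9 points |
| 10 | 0.427 | 0.526 | 9.9 points |
| 14 | 0.398 | 0.537 | 13.9 points |

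The censored values sit a little above 0.50 because the k patients are alive up to removal by construction. With k = 1 or 2 and m = 3 the gap is about 1 to 2 points. With m = 6 it is about 2.5, 5 and 7 points for k = 5, 10 and 14. With m = 12 (same hazard as the others) it is about 0 at each k.

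**5. The same question on median OS.** Assumptions: median 9 or 12 months; 5 to 20% of patients needing a prohibited treatment in months 0 to 6 if alive (about 2 to 8 of 48); hazard afterwards 1, 2 or 3 times that of the others; 36 months of follow-up. Censoring at removal overstates the median by about 0 months at hazard ratio 1, 0.2 to 1.3 at 2, and 0.4 to 2.0 at 3.

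**6. The trigger conflicts with other text.**

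- Glucocorticoids: the 5.5.2 bullet allows them only for suspected immune events, with physiologic doses after Sponsor consultation. Section 6.2.1.2 says "generally a single agent antiemetic should be considered e.g., dopamine receptor antagonist, antihistamines or dexamethasone", and Table 7 allows stable corticosteroids for brain metastases.
- Radiation: the bullet excepts a symptomatic solitary lesion or the brain. Table 6 excepts palliative radiotherapy generally. Table 7 allows it for painful bone metastases present at baseline and expects study treatment to restart. A patient irradiated at two such sites could be removed under one entry and restarted under another.

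**The case against.** The strongest reply is that nothing in 5.5.2 says follow-up stops. The loss of follow-up is borrowed from 5.7, which is written for patients who withdraw consent, while every explicit follow-up rule points the other way. That is fair: a reader might infer that the plan does end PFS and OS follow-up, but the documents support this only as one literal reading. What stands is that the clause invites that reading and nothing in 5.5.2 rules it out.

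A reader might also infer that the patients lost are those doing worst. The documents do not establish this. The prohibition covers only screening and treatment, and the text after Table 7 says no therapy is prohibited in post-treatment follow-up. Next-line therapy after confirmed progression and discontinuation therefore falls outside the clause. Section 5.8 already counts clinical deterioration after two doses as progression. Live vaccines, also on the list, have no evident link to prognosis.

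The larger bias figures are assumption-driven. A residual median of 3 months against 12 is a hazard ratio of 12/3 = 4, applied to 5/48 = 10% up to 14/48 = 29% of patients. A reader might take the bias to be always upward; with equal hazard it is about nil, so the range must include zero.

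Finally, PFS and OS are secondary and descriptive, with no test or decision rule attached. This limits the consequence but does not remove the contradiction.

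**Conclusion.** The clause is wrong as written: it contradicts the paragraph that follows it and the sections that govern discontinuation, withdrawal and survival follow-up. It is a conflicting instruction on a point that affects secondary endpoints, not merely missing detail. It deserves correction but is not critical to the trial's main conclusion.

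Its effect on OS, and on PFS for the narrower set of triggers, depends on how sites read it, how many patients are affected and how they fare afterwards. None of these is given. Under the assumed inputs the overstatement of 12-month OS lies between about 0 and 14 points, and no single figure can be defended.

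A reader might go further and conclude that the primary result is compromised. The documents do not support that: n = 48 and the boundary of 10 responses are unchanged, and counting missing responses as failures is conservative.

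**What to change.** In 5.5.2, replace the removal clause with wording to this effect: whatever is decided about study treatment, the participant remains on study, with disease imaging under 6.1.2.6.3 and survival contact under 6.1.5.3.3, until the end-points of follow-up already stated in those sections and in 5.6 (including death, withdrawal of consent, loss to follow-up and end of study). The wording should not force treatment to stop, because the next paragraph of 5.5.2 allows continuation by agreement. It should not make withdrawal of consent the only end of follow-up, because the other sections list more.

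Separately, reconcile the 5.5.2 glucocorticoid and radiation bullets with section 6.2.1.2 and Tables 6 and 7, so that no treatment is both provided for and a reason for removal. Which clinical rule should prevail is for the sponsor and investigators; this review takes no view.

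The cost is a wording amendment. The imaging and the 12-weekly calls already exist, and no design figure changes. It should be made while follow-up is still possible.

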5.5.3 Rescue Medications & Supportive Care

Participants should receive appropriate supportive care measures as deemed necessary by the treating investigator. Suggested supportive care measures for the management of AEs with potential immunologic etiology are outlined along with the dose modification guidelines in Section 5.2.2 (Table 5). Where appropriate, these guidelines include the use of oral or IV treatment with corticosteroids, as well as additional anti-inflammatory agents if symptoms do not improve with administration of corticosteroids. Note that several courses of steroid tapering may be necessary as symptoms may worsen when the steroid dose is decreased. For each disorder, attempts should be made to rule out other causes such as metastatic disease or bacterial or viral infection, which might require additional supportive care. The treatment guidelines are intended to be applied when the Investigator determines the events to be related to pembrolizumab and/or olaparib.

Note: If after the evaluation of the event, it is determined not to be related to pembrolizumab, the Investigator does not need to follow the treatment guidance. Refer to (Table 5) in Section 5.2.2 for guidelines regarding dose modification and supportive care.

It may be necessary to perform conditional procedures such as bronchoscopy, endoscopy, or skin photography as part of evaluation of the event.

5.6 Participant Discontinuation Criteria

Discontinuation of study intervention does not represent withdrawal from the study.

Participants may discontinue study treatment at any time for any reason or be dropped from the study treatment at the discretion of the investigator should any untoward effect occur. In addition, a participant may be discontinued from study treatment by the investigator or the Sponsor if study treatment is inappropriate, the trial plan is violated, or for administrative and/or other safety reasons. Specific details regarding procedures to be performed at study treatment discontinuation are provided in Section 7.1.4 – Other Procedures.

A participant must be discontinued from study treatment but continue to be monitored in the study for any of the following reasons:

- The participant or participant's legally acceptable representative requests to discontinue study treatment
- Confirmed radiographic disease progression outlined in Section 7.1.2.6
- Any progression or recurrence of any malignancy, or any occurrence of another malignancy that requires active treatment
- Unacceptable adverse experiences as described in Section 5.2.2.
- The participant has a medical condition or personal circumstance which, in the opinion of the investigator and/or sponsor, placed the participant at unnecessary risk from continued administration of study treatment.
- The participant has a confirmed positive serum pregnancy test
- Noncompliance with study treatment or procedure requirements
- Recurrent Grade 2 pneumonitis
- Discontinuation of treatment may be considered for participants who have attained a confirmed complete response (CR) and have been treated for at least 8 cycles (at least 24 weeks), receiving 2 cycles of the combination including 2 doses of pembrolizumab and at least 80% of the planned doses of olaparib beyond the date when the initial CR was declared. These participants may be eligible for second course treatment described in Section 5.2.3.
- The participant is lost to follow-up
- Completion of 35 treatments (approximately 2 years) with pembrolizumab

Note: The number of treatments is calculated starting with the first dose. Participants who stop the combination or pembrolizumab after receiving 35 doses may be eligible for retreatment if they progress after stopping study treatment provided they meet the requirements detailed in Section 5.2.3. Participants may be retreated in the Second Course Phase (Retreatment) for up to an additional 17 cycles (approximately 1 year).

- Administrative reasons
- The End of Treatment and Follow-up visit procedures are listed in Section 8 (Protocol Flow Chart) and Section 10.0.1 (Visit Requirements). After the end of treatment, each subject will be followed for 30 days for adverse event monitoring (serious adverse events will be collected for 90 days after the end of treatment). Subjects who discontinue for reasons other than progressive disease will have post-treatment follow-up for disease status until disease progression, initiating a non-study cancer treatment, withdrawing consent or becoming lost to follow-up. After documented disease progression each subject will be followed by telephone for overall survival until death, withdrawal of consent, or the end of the study, whichever occurs first.

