6.1.2.6 Tumor Imaging and Assessment of Disease

Tumor assessments will be performed by computer tomography (CT), PET/CT or Magnetic Resonance Imaging (MRI).

Tumor imaging is strongly preferred to be acquired by computed tomography (CT). For the abdomen and pelvis, contrast-enhanced magnetic resonance imaging (MRI) may be used when CT with iodinated contrast is contraindicated, or when local practice mandates it. MRI is the strongly preferred modality for imaging the brain. The same imaging technique regarding modality, ideally the same scanner, and the use of contrast should be used in a participant throughout the study to optimize the reproducibility of the assessment of existing and new tumor burden and improve the accuracy of the assessment of response or progression based on imaging.

Scans obtained prior to consenting will be allowed, as long as performed within 21 days of study initiation. CT Scans or MRI's will be repeated every 3 cycles (3 weeks cycles); that is before every fourth dose of pembrolizumab in order to assess response to therapy. Tumor imaging will only be required every 12 weeks for patients that have been on treatment for more than 1 year. Immune Response Evaluation Criteria (iRECIST) [36] will be utilized for assessment of response to therapy.

Expedited confirmation of measurable disease based on RECIST 1.1 at Screening should be used to determine participant eligibility. Confirmation that the participant's imaging shows at least 1 lesion that is appropriate for selection as a target lesion per RECIST 1.1 is highly recommended prior to participation allocation.

Participant eligibility will be determined using local assessment (Investigator assessment) based on RECIST 1.1. In addition, images (including via other modalities) that are obtained at an unscheduled time point to determine disease progression, as well as imaging obtained for other reasons, but which demonstrate radiologic progression, should also be used to determine progression.

When the Investigator identifies radiographic progression per RECIST 1.1, efforts should be made to verify radiologic PD. Treatment should continue until PD has been verified. Regardless of whether PD is verified, if the Investigator considers the participant has progressed, but elects to implement iRECIST, the Investigator will assess for confirmation of progression by iRECIST at subsequent time points.

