6.1.2.6.5 RECIST 1.1 Assessment of Disease

RECIST 1.1 will be used as the primary measure for assessment of tumor response, date of disease progression, and as a basis for all protocol guidelines related to disease status (eg, discontinuation of study treatment). Although RECIST 1.1 references a maximum of 5 target lesions in total and 2 per organ, the Sponsor allows a maximum of 10 target lesions in total and 5 per organ, if clinically relevant to enable a broader sampling of tumor burden.

6.1.2.6.6 iRECIST Assessment of Disease

iRECIST is based on RECIST 1.1 but adapted to account for the unique tumor response seen with immunotherapeutic drugs. When clinically stable, participants should not be discontinued until progression is confirmed by the Investigator, working with local radiology, according to the rules below. This allowance to continue treatment despite initial radiologic PD takes into account the observation that some participants can have a transient tumor flare in the first few months after the start of immunotherapy, and then experience subsequent disease response.

[figure not shown]
A description of the adaptations and iRECIST process is provided in Appendix 4, with additional detail in the iRECIST publication [Seymour et al., 2017]. iRECIST will be used by the Investigator to assess tumor response and progression, and make treatment decisions.

Table 8 Imaging and Treatment after First Radiologic Evidence of Progressive Disease

	Clinically Stable		Clinically Unstable	
	Imaging	Treatment	Imaging	Treatment
First radiologic evidence of PD by RECIST 1.1	Repeat imaging at 4 to 8 weeks to confirm PD	May continue study treatment at the Investigator's discretion while awaiting confirmatory tumor imaging by site by iRECIST	Repeat imaging at 4 to 8 weeks to confirm PD per Investigator's discretion only	Discontinue treatment
Repeat tumor imaging confirms PD (iCPD) by iRECIST per Investigator assessment	No additional imaging required	Discontinue treatment (exception is possible upon consultation with Sponsor)	No additional imaging required.	Not applicable
Repeat tumor imaging shows iUPD by iRECIST per Investigator assessment	Repeat imaging at 4 to 8 weeks to confirm PD. May occur at next regularly scheduled imaging visit	Continue study treatment at the Investigator's discretion	Repeat imaging at 4 to 8 weeks to confirm PD per Investigator's discretion only	Discontinue treatment

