7.0 STATISTICAL ANALYSIS PLAN

7.1 Statistical Analysis Plan Summary

7.2 Statistical Analysis Plan

Sample size calculation: Single-Stage design will be used for this study [A'Hern, 2001; Fleming, 1982]. The study will require 48 subjects to decide whether the proportion responding (P), is less than or equal to 0.130 or greater than or equal to 0.280. If the number of responses is 10 or more, the hypothesis that $P \leq 0.130$ is rejected with a target error rate of 0.100 and an actual error rate of 0.087. If the number of responses is nine or less, the hypothesis that $P \geq 0.280$ is rejected with a target error rate of 0.100 and an actual error rate of 0.099.

Efficacy analyses: The iORR will be defined as the proportion of patients with an “immune” complete response (iCR) or “immune” partial response (iPR). For the primary iORR analysis in all the treated population, patients with an iCR or iPR will be counted as successes and all other patients (including those with missing response information) will be counted as failures. The percentage of iORR with its 95% confidence interval (CI) will be presented.

Progression free survival (PFS) will be defined among all treated patients as the time from first dose of study drug until the first date of either disease progression or death due to any cause. The date of disease progression will be defined as the earliest date of disease progression based on central review. For patients whose disease has not progressed at the time of the analysis, censoring will be performed using the date of the last valid disease assessment. The data will be analyzed by the Kaplan-Meier method. The median PFS time and 95% CI will be recorded.

Overall survival (OS): Median OS will be defined as the time from the beginning of study drug treatment until death due to any cause. For patients who have not died at the time of the analysis, censoring will be performed using the date the patient was last known to be alive. The data will be analyzed by the Kaplan-Meier method. The median OS and 95% CI will be recorded.

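### The mandatory stop list in 5.6 includes any progression, with no confirmation required, and so conflicts with the imaging sections for a clinically stable patient at first progression

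*Combined protocol and SAP*

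**What the plan says.** Section 5.6 introduces its list with "A participant must be discontinued from study treatment but continue to be monitored in the study for any of the following reasons". Two adjacent items concern progression. The earlier one requires confirmed radiographic progression and refers to Section 7.1.2.6; in the current numbering the imaging text is 6.1.2.6. The next item reads "Any progression or recurrence of any malignancy, or any occurrence of another malignancy that requires active treatment" and sets no confirmation requirement.

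Other sections address the same situation:

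- Section 6.1.2.6, after the investigator identifies RECIST 1.1 progression: "Treatment should continue until PD has been verified".
- Section 6.1.2.6.6: "When clinically stable, participants should not be discontinued until progression is confirmed by the Investigator".
- Section 6.1.2.6.2 and Table 8 (clinically stable column) let the investigator decide whether treatment continues while confirmation is awaited. Appendix 4 also makes this the investigator's decision.
- Section 2.0 allows treatment past an initial iRECIST progression case by case, where benefit and tolerance are documented.
- Section 6.1.2.6.5 makes RECIST 1.1, which has no separate confirmation step for progression in this protocol, the basis for stopping treatment.

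The primary endpoint is the immune overall response rate by iRECIST (3.1, 7.2).

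**The concern.** Take a clinically stable patient whose week 9 scan shows progression for the first time. The 5.6 item says treatment must stop, 6.1.2.6 and 6.1.2.6.6 say it should not stop yet, and 6.1.2.6.2, Table 8 and Appendix 4 say it may continue. Section 2.1 describes the trial as multi-center, so sites could resolve this differently.

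The conflict reaches the primary endpoint because of how iRECIST is used here. Appendix 4 states that nothing distinguishes iRECIST from RECIST 1.1 until RECIST 1.1 progression occurs. The immune criterion can therefore add a responder only among patients assessed after a first progression, and a stop at first progression acts on that group. If such responses go unrecorded, the estimated iORR is biased downward and an active combination is somewhat more likely to be declared inactive.

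**Working it through.** **Step 1: is there a reading of 5.6 without conflict?** If the *any progression* item covers the cervical cancer, every patient with confirmed radiographic progression already meets it, so the confirmed-progression item adds nothing. If it covers only other malignancies, both items have a function, but the text does not say so. The closing words about active treatment might qualify the whole item or only its second half. Even on the wider reading they would not clearly exempt a progressing cervical cancer. The ambiguity sits inside 5.6 before any other section is consulted.

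**Step 2: how could a response be missed?** Three provisions act in sequence.

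- The closing text of 5.6 moves patients to telephone follow-up for survival after documented progression.
- Section 6.1.2.6.3 makes the discontinuation scan the last one required when a patient stops for documented progression and the investigator does not implement iRECIST.
- Section 7.2 counts every treated patient without a recorded iCR or iPR as a failure, including those with missing response data.

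A patient stopped at first progression under 5.6 may therefore have no later scan and would be counted as a non-responder.

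**Step 3: reproduce the design.** Inputs from 7.2: n = 48, null rate 0.130, target rate 0.280, success at 10 or more responses. With X ~ Binomial(48, p):

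- α = P(X ≥ 10 | p = 0.13) = 0.0865. The plan states 0.087.
- Power = P(X ≥ 10 | p = 0.28) = 0.9005, so β = 1 − 0.9005 = 0.0995 (0.09946 to five decimals). The plan states 0.099.

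The plan's figures are reproduced.

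**Step 4: sensitivity.** Let f be the share of true responders lost. It is the product of three unknowns: the share whose response follows a first progression, the share of those stopped under 5.6, and the share of those never rescanned. The effective response rate is p(1 − f). The documents give no value for any component, so every f below is an assumption. Expected responders at the target are 48 × 0.28 = 13.44.

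| f (assumed) | Responders lost, 13.44 × f | Target rate, 0.28(1 − f) | Power | Null rate, 0.13(1 − f) | α |
|---|---|---|---|---|---|
| 0 | 0 | 0.2800 | 0.9005 | 0.1300 | 0.0865 |
| 2% | 0.27 | 0.2744 | 0.885 | 0.1274 | 0.078 |
| 5% | 0.67 | 0.2660 | 0.858 | 0.1235 | 0.066 |
| 10% | 1.34 | 0.2520 | 0.804 | 0.1170 | 0.049 |

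The power loss is about 1.6 points at 2% (0.9005 − 0.885), 4.2 points at 5% and 9.7 points at 10%. Type I error falls in every row.

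**The case against.** The strongest reply is contextual. The confirmed-progression item is specific to radiographic progression and points to the imaging section. A site could reasonably apply it to the cervical cancer and take the next item as addressing other malignancies. Systematic stopping at first progression is then speculative. This stands as a reason not to assume the worst. It does not remove the conflict, because the item says any malignancy and the list is mandatory.

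A second reply also stands in part. Table 8, 6.1.2.6.2 and Appendix 4 already leave treatment past a first progression to the investigator. iORR and PFS would therefore mix stopped and continued patients even if the 5.6 item were deleted, and not all of that mixture can be charged to 5.6.

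A reader might also draw stronger conclusions that the documents do not support:

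- *That the imaging sections forbid stopping.* They say treatment should continue, or may continue at discretion. None says it must.
- *That sites following 5.6 cannot observe these responses.* Section 5.6 separates stopping treatment from leaving the study and keeps patients monitored. No section prohibits a later scan. Table 8 allows discretionary repeat imaging in clinically unstable patients already taken off treatment, and provides for a later iSD, iPR or iCR. Observation is at risk, but it is not ruled out.
- *That late responses in general are lost.* Responses that emerge from stable disease are unaffected; only those after a first progression are exposed.
- *That 3.1 would have to say iORR excludes responses after progression if the stricter rule were kept.* This does not follow, since a scan after stopping could still record one.
- *That power drops to about 0.84 or 0.75.* Those are the values at response rates of 0.26 and 0.24, roughly one or two patients of 48 lost. One patient is 1/13.44 = 7% of expected responders and two are 2/13.44 = 15%. That is high for an event Section 2.0 calls rare, and it supposes that every such patient is stopped and none is rescanned.

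**Conclusion.** The contradiction is real and can be shown from the text alone. For a clinically stable patient at first progression, the 5.6 item, read literally, requires a stop that 6.1.2.6 and 6.1.2.6.6 advise against and that 6.1.2.6.2, Table 8, Appendix 4 and Section 2.0 make a matter of judgment. Section 6.1.2.6.5 adds to the conflict by tying discontinuation to RECIST 1.1.

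Its effect on the primary endpoint is plausible but cannot be sized from the documents. On the assumed range of 2% to 10% of responders lost, power at 28% is 0.885 to 0.804 instead of 0.9005. These figures also assume that the 28% target includes responses after a first progression, which 7.2 does not state; the monotherapy benchmark in 4.1.1 is a RECIST 1.1 rate. The direction is conservative: iORR is understated and type I error does not rise. This should be corrected by amendment. It does not undermine the sample size calculation.

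**What to change.** Reconcile 5.6 with 2.0, 6.1.2.6, 6.1.2.6.2, 6.1.2.6.5, 6.1.2.6.6, Table 8 and Appendix 4, so that all give one instruction on when progression of the cervical cancer ends study treatment. Which instruction applies is the sponsor's clinical decision. State explicitly whether the *any malignancy* item in 5.6 covers the cancer under study. All the listed sections need to be in scope, since amending only some would leave the conflict in place elsewhere.

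Whichever instruction is chosen, add to 7.2 a count of patients whose treatment stopped at unconfirmed progression, so that a reader of the iORR can see how many were exposed to this loss.

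The cost is a short amendment and one line in a table. The sample size, cut-off and stated error rates do not change.
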